4.2 Exclusion Criteria

- 1) Radiation to any area of the body ≤ 28 days prior to randomization.
- 2) Any other active malignancy with the exception of adequately treated basal or squamous cell skin cancer or superficial bladder cancer. Autoimmune disease: Patients with a history of inflammatory bowel disease are excluded from this study, as are patients with a history of symptomatic disease (eg, rheumatoid arthritis, systemic progressive sclerosis [scleroderma], systemic lupus erythematosus, autoimmune vasculitis [eg, Wegener's Granulomatosis]); motor neuropathy considered of autoimmune origin (e.g. Myasthenia Gravis, Guillain-Barre Syndrome). Those with immune-mediated skin toxicity (i.e. Toxic Epidermal Necrolysis, Stevens-Johnson Syndrome) will also be excluded.
- 3) Any underlying medical or psychiatric condition, which in the opinion of the investigator will make the administration of ipilimumab hazardous or obscure the interpretation of AEs, such as a condition associated with frequent diarrhea.
- 4) Any non-oncology vaccine therapy used for prevention of infectious diseases (for up to 1 month before or after any dose of ipilimumab).
- 5) A history of prior treatment with ipilimumab or prior CD137 agonist or CTLA-4 inhibitor or agonist.
- 6) Concomitant therapy with any of the following: IL-2, interferon, or other nonstudy immunotherapy regimens; cytotoxic chemotherapy; immunosuppressive

agents (OTC/herbal/prescribed); immunostimulant agents, other than the study agent; other investigational therapies; or chronic use of systemic corticosteroids (greater than prednisone 10 mg orally per day, or its equivalent).

7) Prisoners or patients who are compulsorily detained (involuntarily incarcerated) for treatment of either a psychiatric or physical (i.e., infectious) illness.

4.3 Data Safety Monitoring Plan

The Data and Safety Monitoring Plan is outlined in a separate document and is NCI approved.

5 STUDY THERAPY

All patients will receive ipilimumab 10 mg/kg IV over 90 minutes on day 1 of each 21-day cycle for four cycles. Those patients who have not progressed (radiographically) will also receive the same dose of ipilimumab once every three months for an additional four doses. Each patient's available lab results (i.e. chemistries and blood counts) will be reviewed prior to each ipilimumab infusion.

5.1 **Ipilimumab**

Each patient will receive ipilimumab 10 mg/kg IV over 90 minutes (not bolus or IV push).

Ipilimumab (BMS-734016) is a human immunoglobulin G (IgG1) κ anti-CTLA-4 monoclonal antibody (mAb). In vitro studies were performed with ipilimumab to demonstrate that it is specific for CTLA-4, actively inhibits CTLA-4 interactions with B7.1 and B7.2, does not show any cross-reactivity with human B7.1, B7.2 negative cell lines, and stains the appropriate cells without nonspecific cross-reactivity in normal human tissues, as demonstrated by immunohistochemistry. Ipilimumab does cross-react with CTLA-4 in non-human primates, including cynomolgus monkeys.

5.1.1 Dose Calculations

Dose calculations will be based on the weight obtained on Cycle 1 Day 1 and will only change if the weight increases or decreases by more than 10%.

Calculate **Total Dose** as follows:

Patient body weight in kg x [10 mg] = total dose in mg

Calculate **Total Infusion Volume** as follows:

Total dose in mg \div 5 mg/mL = infusion volume in mL

Calculate **Rate of Infusion** as follows:

Infusion volume in $mL \div 90$ minutes = rate of infusion in mL/min.

For example, a patient weighing 114 kg (250 lb) would be administered 1140 mg of ipilimumab (114 kg x 10 mg/kg = 1140 mg) with an infusion volume of 228 mL (1140 mg \div 5 mg/mL = 228 mL) at a rate of approximately 2.5 mL/min (228 mL \div 90 minutes) in 90 minutes.

5.1.2 Storage, Preparation, and Administration

Ipilimumab Injection, 50 mg/vial (5 mg/mL) or 200 mg/vial (5 mg/mL), must be stored refrigerated (2°C to 8°C) and protected from light. Ipilimumab injection must not be frozen. Partially used vials or empty vials of Ipilimumab Injection should be discarded at the site according to appropriate drug disposal procedures.

Ipilimumab injection may be diluted in 0.9% Sodium Chloride Injection, USP or 5% Dextrose Injection, USP to concentrations between 1 mg/mL and 4 mg/mL and stored in PVC, non-PVC or glass containers for up to 24 hours at 2-8°C or RT/RL.

Recommended safety measures for preparation and handling include protective clothing, gloves, and safety cabinets.

5.1.2.1 Preparation and Administration Guidelines

The supplies needed for ipilimumab preparation and administration include calibrated syringes and infusion containers. The product may be infused using a volumetric pump at the protocol-specific dose(s) and rate(s) through a PVC IV solution infusion set with a $0.2~\mu m$ or $1.2~\mu m$ in-line polyethersulfone or $1.2~\mu m$ positively charged nylon filter to complete the infusion in 90 minutes, with a 10-mL normal saline flush at the completion of the infusion.

- 1) As ipilimumab is stored at refrigerated temperatures (2-8°C), allow the appropriate number of vials of ipilimumab to stand at room temperature for approximately five minutes.
- 2) Aseptically withdraw the required volume of ipilimumab solution into a syringe. Insert the needle at an angle into the ipilimumab vial by placing the needle bevel side down against the glass, with the tip touching the neck of the vial. The initial solution concentration is 5 mg/mL. [Note: A sufficient excess of ipilimumab is incorporated into each vial to account for withdrawal losses].

- 3) Ensure that the ipilimumab solution is clear colorless, essentially free from particulate matter on visual inspection. If multiple vials are needed for a subject, it is important to use a separate sterile syringe and needle for each vial to prevent problems such as dulling of needle tip, stopper coring, repeated friction of plunger against syringe barrel wall, etc.
- 4) Inject ipilimumab solution withdrawn into an appropriate size evacuated infusion bag to produce a final infusion volume that has been calculated from the weight of the patient. For example, if preparing a 10mg/kg treatment for a 65 kg patient you will use 13 vials (or 650 mg), the drug solution volume will be 10 mL per vial or 130 mL total
- 5) If the total dose calculates to less than 90 mL of solution then the total dose needed should be diluted to a total volume of 90 mL in 0.9% sodium chloride.
- 6) Mix by GENTLY inverting several times. DO NOT shake.
- 7) Visually inspect the final solution. If the initial diluted solution or final dilution for infusion is not clear or contents appear to contain precipitate, the solution should be discarded.
- 8) Do not draw into each vial more than once. Any partial vials should be safely discarded and should not be stored for reuse.

Ipilimumab should be administered under the supervision of a physician experienced in the use of intravenous (IV) agents. Ipilimumab is administered as an IV infusion only.

5.1.3 Dose Modifications

Patients may develop study drug-related toxicities that may require skipping doses or dose discontinuation. Some of these adverse events may be consistent with potentially drug-related immune-mediated phenomena; termed IRAEs (Appendix 3). Details of how to dose study medication in the present of adverse drug reactions that may or may not be IRAEs are addressed below.

Treatment modifications will be made based on specified safety criteria. Patients will delay or discontinue treatment with ipilimumab if they experience at least one adverse event, specified below, considered by the investigator to be certainly, probably, or possibly related to ipilimumab treatment. The following criteria will be used to determine dosing delay, restarting doses, or discontinuing ipilimumab.

There are no dose modifications because Ipilimumab is much less effective at lower doses.

Delay ipilimumab dosing for the following related adverse events:

It may be necessary to skip study drug dosing for the following related adverse event(s):

- Any ≥ Grade 2 non-skin related adverse event (including IBEs), except for laboratory abnormalities
- Any ≥ Grade 3 laboratory abnormality.

It is necessary to skip study drug dosing for the following adverse events:

• Any \geq Grade 3 skin-related adverse event regardless of causality.

Restart ipilimumab dosing if/when the adverse event(s) resolve(s) to \leq Grade 1 severity or returns to baseline within 3 weeks of initial dose administration:

- If the *adverse event has resolved*, restart ipilimumab dosing at the next scheduled time point per protocol.
- If the *adverse event has not resolved* in the protocol-specified dosing window (3 weeks [+/- 3 days], the next scheduled dose will be *omitted*.

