 - Serum PSA will be drawn every 6 weeks for weeks 12-24, then every 12 weeks.
 - Complete blood count with automatic differential, comprehensive chemistry panel and Autoimmune Panel (TSH, free T4) will be obtained prior to administration of each dose of ipilimumab, which will be given to eligible patients every 12 weeks beginning at week 24.

- Available lab results (i.e. chemistries and blood counts) will be reviewed prior to administration of ipilimumab.
- o Imaging and Diagnostic: A radionuclide bone scan and CT scan (chest, abdomen and pelvis) will be obtained at baseline, week 12, week 24, and every three months thereafter until radiographic progression. Scans may be obtained sooner for concerning symptoms.

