5.1.5 Permanent Discontinuation of Ipilimumab

5.1.5.1 Permanent Discontinuation for Related Adverse Events

- Any ≥ Grade 2 eye pain or reduction of visual acuity that does not respond to topical therapy and does not improve to ≤ Grade 1 severity within 2 weeks of starting therapy, OR, requires systemic treatment.
- Any \geq Grade 3 bronchospasm or other hypersensitivity reaction.
- Any other \geq Grade 3 non-skin related adverse event with the exception of events listed under "No Discontinuation" (below).
- Any adverse event, laboratory abnormality or intercurrent illness which, in the judgment of the investigator, presents a substantial clinical risk to the patient with continued dosing.

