5.1.5.2 Exceptions to Permanent Discontinuation

- Potentially reversible inflammation (< Grade 4), attributable to a local anti-tumor reaction and a potential therapeutic response. This includes inflammatory reactions at sites of tumor resections or in draining lymph nodes, or at sites suspicious for, but not diagnostic of metastasis.
- Hospitalization for ≤ Grade 2 adverse events where the primary reason for hospitalization is to expedite the clinical work-up.
- Patients with the following conditions where in the investigator's opinion continuing study drug administration is justified:
 - Ocular toxicity that has responded to topical therapy.
 - Endocrinopathies where clinical symptoms are controlled with appropriate hormone replacement therapy. Note: Ipilimumab may not be restarted while the patient is being treated with systemic corticosteroids except for patients on stable doses of hormone replacement therapy such as hydrocortisone.

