Patients with colitis should discontinue any non-steroidal anti-inflammatory medications or any other medications known to exacerbate colitis symptoms. Investigators should use their clinical judgment as to whether corticosteroids are necessary to treat colitis associated with ipilimumab therapy and as to what dose should be used. As guidance prior experience suggests that colitis manifested as \geq Grade 3 diarrhea requires

corticosteroid treatment. For severe symptoms, prednisone 60 mg or equivalent may be required to control initial symptoms and the dose should be gradually tapered over at least one month in duration. Lower doses of prednisone may be considered for less severe cases of colitis. It is suggested that prednisone (for oral administration) or solumedrol (for intravenous administration) be corticosteroid of choice in the treatment of colitis.

Liver: Elevation of LFTs ≥ 3 fold from baseline should instigate an investigation into the underlying etiology for suspected IRAEs. Neoplastic, concurrent medications, viral hepatitis, and toxic etiologies should be considered and addressed, as appropriate. Imaging of the liver, gall bladder, and bile duct should be performed to rule out neoplastic or other causes for the increased LFTs. An ANA, pANCA, and anti-smooth muscle antibody test should be performed if an autoimmune etiology is considered. Consultation with a hepatologist is appropriate for a suspected liver IRAE and a biopsy should be considered.

Patients presenting with right upper-quadrant abdominal pain and/or unexplained nausea or vomiting should have LFTs performed immediately and reviewed before administering the next dose of study drug. Treating physicians should discuss, with the CRO Medical Monitor, unexplained increases in LFTs ≥ 3 fold from baseline prior to any additional study drug administration.

Pancreas: Symptoms of abdominal pain associated with elevations of amylase and lipase, suggestive of pancreatitis, may rarely be associated with anti-CTLA-4 monoclonal antibody administration. The differential diagnosis of acute abdominal pain should include pancreatitis. Appropriate workup should include serum amylase and lipase tests.

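### Sections 5.1.3 (hold and restart) and 5.1.5.1 (permanent stop) overlap from Grade 3 upward with no stated precedence, most clearly for laboratory abnormalities

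*Combined protocol and SAP*

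**What the plan says.** Section 5.1.3 opens by saying that its criteria decide delay, restart and discontinuation together. It allows no dose reduction. Under the permissive heading that a dose may need to be skipped, it lists two kinds of related event: "Any ≥ Grade 2 non-skin related adverse event (including IBEs), except for laboratory abnormalities" and "Any ≥ Grade 3 laboratory abnormality". Neither has an upper grade. Once the event has come down to Grade 1 or baseline within the window, the site is told to "restart ipilimumab dosing at the next scheduled time point per protocol". If it has not resolved in the window, only the next dose is omitted.

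Section 5.1.5.1 lists related events that end ipilimumab for good. Its third bullet covers any other "Grade 3 non-skin related adverse event with the exception of events listed under" a list named 'No Discontinuation'. No heading has that name; the list that follows is 5.1.5.2. That list exempts local anti-tumour inflammation below Grade 4, admission for work-up of events up to Grade 2, ocular toxicity that has responded to topical therapy, and endocrinopathy controlled by hormone replacement. It does not mention laboratory abnormalities or events that have since resolved. The last bullet of 5.1.5.1 allows a permanent stop for an adverse event, laboratory abnormality or illness that the investigator judges a substantial risk. Section 5.1.4 has a similar judgement clause.

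**The concern.** A related non-skin event of Grade 3 or 4 that resolves promptly satisfies both sections. One tells the site to restart; the other tells it never to dose again. Because the dose cannot be reduced, the choice is the full 10 mg/kg or nothing.

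For laboratory abnormalities the overlap is harder to resolve. The 5.1.3 hold starts at Grade 3, the same grade at which the third bullet of 5.1.5.1 starts. Section 5.1.3 expressly removes laboratory abnormalities from its own non-skin bullet, but 5.1.5.1 does not. Two sites could each follow the protocol and treat the same Grade 3 transaminase value in opposite ways.

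What is at stake is safety on re-dosing, consistent handling across sites, exposure and discontinuation counts, and membership of the per-protocol population in section 8.4, which depends on receiving the prescribed dose.

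**Working it through.** The plan gives no figure here to reproduce. The check sets the rules side by side, then sizes the group concerned.

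**Text comparison**

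| Related event | 5.1.3 | 5.1.5.1, third bullet |
|---|---|---|
| Non-skin clinical, Grade 2 | may skip, restart on recovery | does not apply |
| Non-skin clinical, Grade 3-4, resolved, not exempt | may skip, restart | permanent stop |
| Grade 3 event exempted by 5.1.5.2 | may skip, restart | excepted |
| Laboratory, Grade 3 or higher | may skip, restart | permanent stop if it counts as an adverse event; otherwise silent |
| Skin, Grade 3 or higher | must skip, restart | not covered |

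Rows two and four are the overlap. In row two, letting 5.1.3 prevail would leave the third bullet of 5.1.5.1 with almost no effect, so a stop is the likely intent. In row four, letting 5.1.5.1 prevail would leave the 5.1.3 laboratory bullet with almost no effect. A bare precedence sentence would therefore repair row two but, without a laboratory exception, would undo the 5.1.3 laboratory rule.

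**Number of men to whom the overlap could apply**

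Inputs: Table 1 (section 1.3.5.2), melanoma, 10 mg/kg, N = 71, Grade 3-4 immune-related events: overall 25.4%, skin 4.2%, hepatic 2.8%, endocrine 1.4%. Accrual is 30 (section 8.3). Applying melanoma rates to these men is an assumption.

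- Minimum non-skin, if every man with a skin event had no other Grade 3-4 event: (0.254 − 0.042) × 30 = 6.36. As 15 of 71, the exact 95% interval scaled to 30 men is 3.7 to 9.7.
- Maximum, if every man with a skin event also had a non-skin one: 0.254 × 30 = 7.62. As 18 of 71, the interval is 4.7 to 11.1.
- Minimum less endocrine events, some of which 5.1.5.2 may exempt: (0.212 − 0.014) × 30 = 5.94.
- Chance of at least one such man at the minimum rate: 1 − (1 − 0.212)^30 = 0.999.
- Hepatic events, a rough proxy for the laboratory overlap: 0.028 × 30 = 0.84 men; 2 of 71 gives an interval of 0.1 to 2.9.

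**Does the steroid rule settle it?**

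Section 5.1.5.2 notes that "Ipilimumab may not be restarted while the patient is being treated with systemic corticosteroids", apart from stable hormone replacement. The note sits under the endocrinopathy exception, so whether it applies generally is open. For severe colitis, Appendix 3 advises that "the dose should be gradually tapered over at least one month in duration". If both apply, restart is postponed, but neither text says whether it may happen at all. With induction doses on days 0, 21, 42 and 63, onset 1 to 20 days after a dose and a 30-day minimum taper:

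- Onset after dose 1: clear on day 31 to 50, leaving 2 to 1 induction doses.
- Onset after dose 2: clear on day 52 to 71, leaving 1 to 0.
- Onset after dose 3 or 4: none left.

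Steroid treatment would thus remove much of the difference during induction.

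**The case against.** The best defence is that these are tiers. Delay and permanent discontinuation are separate outcomes; the 5.1.3 wording is permissive; 5.1.5.1 is headed as permanent and has its own exceptions. A man permanently stopped has no next scheduled dose at which to restart. The missing upper grade also has a use, because a Grade 3 event exempted by 5.1.5.2 still needs a hold-and-restart rule. Most of this stands for clinical events: the intent can be inferred. But it is an inference, and a re-dosing rule should state it.

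For laboratory values, the defence is that 5.1.4 and the last bullet of 5.1.5.1 name laboratory abnormalities separately from adverse events, so the third bullet need not reach them. That gives a workable scheme: hold at Grade 3 or higher, restart on recovery, stop on judgement. A reader might infer that no sensible laboratory rule can be extracted; the documents do not support that. But 5.1.3 itself lists laboratory abnormalities among related adverse events, so the opposite reading remains open. The appendix flowcharts are not shown and may add organ-specific guidance. The surviving text of Appendix 5 refers back to the protocol's retreatment criteria, so it may not settle the matter.

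A reader might also infer a separate gap at week 24. Section 5 says "Those patients who have not progressed (radiographically) will also receive the same dose of ipilimumab once every three months for an additional four doses", and 3.3.2 describes a dose "which will be given to eligible patients every 12 weeks beginning at week 24"; neither names toxicity. The documents do not support this as a further defect. A permanent stop covers every later dose, and the induction sentence in section 5 likewise names no toxicity condition without overriding 5.1.3 to 5.1.5.

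**Conclusion.** The overlap is real and no visible sentence resolves it. For clinical events, the likely meaning is hold at Grade 2 and stop at Grade 3, contradicted only by the literal text of 5.1.3. For isolated laboratory abnormalities, the wording allows both outcomes; hold and restart with investigator judgement is the more coherent reading.

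Assuming the Table 1 melanoma rates carry over, about 6 to 8 of 30 men would have a Grade 3-4 non-skin immune-related event to which the overlap could apply. It would be tempting to read that as the number who would be wrongly re-dosed. It is not: the event must also resolve, not be exempt, and be handled under 5.1.3 in preference to 5.1.5.1, and the investigator can still stop for risk. The documents give no rate for those steps.

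The primary ITT analysis and the two-stage design do not change. This is a minor safety clarification. The visible text gives no basis for insisting on an automatic permanent stop for Grade 4 laboratory values.

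**What to change.** - In 5.1.3, limit the first bullet to Grade 2 related non-skin events, plus events of Grade 2 or higher that 5.1.5.2 exempts, still excluding laboratory abnormalities. Add: 'Where 5.1.3 and 5.1.5.1 both apply, 5.1.5.1 prevails.'
- In the third bullet of 5.1.5.1, add: 'except isolated laboratory abnormalities, which follow 5.1.3 and the investigator-judgement bullet below'. Check this against the Appendix 5 flowchart first. Make this change together with the precedence sentence, for the reason given for row four above.
- In the same bullet, replace the 'No Discontinuation' reference with 5.1.5.2.

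The cost is one protocol amendment and site retraining, with no extra patients, visits or tests.

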5.2 Prohibited and Restricted Therapies During the Study

5.2.1 Prohibited Therapies

Patients in this study may not use vaccines for the treatment of cancer or prevention of disease unless indicated as a component of the protocol regimen (including those for common medical conditions) for up to one month pre and post dosing with ipilimumab. Concomitant systemic or local anti-cancer medications or treatments are prohibited in this study while receiving ipilimumab treatments.

Patients may not use any of the following therapies during the study:

- Any non-study anti-cancer agent (investigational or non-investigational)
- Any other investigational agents
- Any other (non-CA184024 related) CTLA-4 inhibitors or agonists
- CD137 agonists
- Immunosuppressive agents
- Immunostimulant agents, other than study medication
- Chronic systemic corticosteroids
- Any non-oncology vaccine therapies used for the prevention of infectious diseases (for up to 30 days prior to or after any dose of study drug).
- Any radiation therapies
- Any herbal product known to decrease PSA (eg., Saw Palmetto, PC-SPES)

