APPENDIX 4 DIARRHEA MANAGEMENT ALGORITHM

Ipilimumab BMS-734016/MDX-010

[figure not shown]
GI Toxicity Management Algorithm

Severity of diarrhea/
colitis

Management Follow-up

Rule out non-inflammatory causes. If non-inflammatory cause, treat accordingly and continue ipilimumab.

Opiates/narcotics mask symptoms of perforation! Infliximab should not be used in case of perforation/sepsis!

Patients on IV steroids may be switched to oral corticosteroid (e.g., prednisone) at an equivalent dose at start of tapering or earlier, once sustained clinical improvement is observed. Lower bioavailability of oral corticosteroids should be taken into account when switching to the equivalent dose of PO corticosteroids.

[figure not shown]
GRADE 1 Increase of < 4 stools per day over baseline; mild increase in ostomy output compared with baseline Baseline GRADE 2 Increase of 4-6 stools per day over baseline; IV fluids indicated < 24 hrs; moderate increase in ostomy output compared to baseline; not interfering with ADL	GRADE 3 Increase of ≥ 7 stools per day over baseline; incontinence; IV fluids ≥ 24 hrs; hospitalization; severe increase in ostomy output compared to baseline; interfering with ADL	GRADE 4 Life-threatening consequences (eg, hemodynamic collapse)	GRADE 5 Death
--	--	--	------------------

Investigator Brock

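### 5.1.3 restarts ipilimumab without regard to steroids, a note of unclear reach in 5.1.5.2 bars restart on steroids, and the 5.2.1 prohibited list does not fit the toxicity algorithms

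*Combined protocol and SAP*

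**What the plan says.** **Restart.** Section 5.1.3 introduces its list as the criteria for delaying, restarting or stopping ipilimumab. The restart test is the grade of the event: once it is Grade 1 or lower, or back to baseline, the site is to "restart ipilimumab dosing at the next scheduled time point per protocol". If it has not settled within the "protocol-specified dosing window (3 weeks [+/- 3 days], the next scheduled dose will be" omitted. Steroid treatment is not part of the test.

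**Steroid note.** Section 5.1.5.2, which lists exceptions to permanent discontinuation, ends with a note under the endocrinopathy bullet: "Ipilimumab may not be restarted while the patient is being treated with systemic corticosteroids except for patients on stable doses of hormone replacement therapy".

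**Permanent stop.** Section 5.1.5.1 ends ipilimumab for related non-skin events of Grade 3 or higher, apart from the listed exceptions.

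**Prohibited therapies.** Section 5.2.1 states "Patients may not use any of the following therapies during the study" and then lists immunosuppressants as an unqualified class and, as a separate item, "Chronic systemic corticosteroids".

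**Treatment of immune events.** Section 5.1.6 allows steroids for an IRAE where clinically needed. Appendix 3 calls for steroids with a slow taper when symptomatic measures do not suffice. For severe colitis symptoms it says "prednisone 60 mg or equivalent may be required to control initial symptoms and the dose should be gradually tapered over at least one month". Appendix 4 says "Infliximab should not be used in case of perforation/sepsis", and a footnote to the Appendix 5 algorithm spells out mycophenolate mofetil.

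**Steroid limit at entry.** Section 4.2 item 6 excludes concomitant immunosuppressive "agents (OTC/herbal/prescribed); immunostimulant agents, other than the study agent; other investigational therapies; or chronic use of systemic corticosteroids" above prednisone 10 mg a day. Section 4.1 criterion 9 uses the same 10 mg figure.

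**The concern.** Two sections answer the same question, whether this man may be given his next dose, with different tests: one looks at event grade, the other at steroid treatment. The steroid note is worded generally but placed under a single type of event, so a site can reasonably read it either as universal or as limited to endocrinopathies. The two readings lead to opposite dosing decisions.

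The prohibited list raises a second question. A site following the management algorithms may reach for an agent that 5.2.1 bars for the whole study. The steroid item in that list also carries no dose, unlike the eligibility criteria.

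At stake is consistent safety dosing between the two sites. The primary analysis is not at stake.

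**Working it through.** The plan states no figure on this point, so there is none to reproduce. The check compares the sections and adds a day count.

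**1. Who can be restarted at all.** Section 5.1.3 provides for skipping doses for related non-skin events of Grade 2 or higher, laboratory abnormalities of Grade 3 or higher, and skin events of Grade 3 or higher. Section 5.1.5.1 then removes most related non-skin events of Grade 3 or higher, and also eye events of Grade 2 or higher that need systemic treatment. What is left is events held but not ended, for example Grade 2 non-skin events (other than those eye events) and Grade 3 skin events.

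**2. Are systemic steroids foreseen for that group?** Yes. Appendix 3 provides for steroids and a slow taper for IRAEs in general, lower prednisone doses for milder colitis, and parenteral steroids for more severe skin symptoms.

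**3. The two tests for a man in that group.** Suppose his event is now Grade 1 and he is still tapering on the next dose date.
- 5.1.3 alone: restart.
- 5.1.5.2 note read as general: do not restart, unless he is on stable hormone replacement.
- 5.1.5.2 note read as endocrine-only: it does not apply, and 5.1.3 governs.

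Nothing in either section selects between these readings.

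**4. Can a taper run past a dose date?** The inputs are the induction interval with its window (5.1.3) and the one-month minimum taper (Appendix 3).
- Latest dose day: 21 + 3 = 24 days after the previous dose.
- Taper of one month, taken as 28 to 31 days and started on the dosing day itself: 28 - 24 = 4 and 31 - 24 = 7 days beyond the window.
- In general, a taper of length L started d days after a dose overlaps the next one when d + L > 24.
- In maintenance the interval is 12 x 7 = 84 days, so a 31-day taper is over in time if begun within 84 - 31 = 53 days. The problem therefore lies mainly in induction.

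The one-month minimum is stated for severe colitis symptoms, which will usually have ended treatment under 5.1.5.1. For other events Appendix 3 gives no taper length. The day count shows that an overlap is possible; it does not show how often one occurs.

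**5. Size.** Table 1 (melanoma, 10 mg/kg) gives Grade 3-4 GI events in 15.5%, and 0.155 x 30 = 4.65 men. These men are mostly outside the group in step 1. Lower-grade GI events in the same table are 39.4 - 15.5 = 23.9%, and 0.239 x 30 = 7.2 men. Grade 3-4 skin events are 4.2%, and 0.042 x 30 = 1.3 men. These two figures only describe where affected men could come from. They assume that melanoma rates carry over, they include Grade 1 events, they leave out other organs, and the share given systemic steroids is not reported. The documents give no rate for the affected group.

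**6. Prohibited list against appendices.** The immunosuppressant item in 5.2.1 has no exception for treating IRAEs, yet the algorithms name two such agents. The algorithm figures are not shown in the copy reviewed, so exactly how those agents are used cannot be checked.

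**7. Steroid wording.** There are three versions: above prednisone 10 mg a day (4.1 and 4.2), chronic use with neither a definition nor a dose (5.2.1), and any systemic steroid other than stable replacement (5.1.5.2).

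**The case against.** The strongest reply is that nothing here forces a contradiction. If the 5.1.5.2 note is general, it is simply a further condition on 5.1.3; if it is endocrine-only, it does not touch other events. Either way the protocol can be followed. This is right as far as it goes, but the text does not say which reading applies, and the dosing decision turns on it.

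A reader might go on to infer several stronger things that the documents do not support:

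- *Every man on a taper is both due for re-dosing and barred from it, some 4 to 5 of 30.* Related non-skin events of Grade 3 or higher normally end treatment under 5.1.5.1, and no listed exception names colitis or diarrhea. The 15.5% is therefore not the number affected.
- *Steroids for immune events are prohibited.* Section 5.2.1 bars only chronic systemic use, and 5.1.6 expressly allows steroids for IRAEs. A time-limited taper is not clearly caught.
- *Men enrolled on prednisone up to 10 mg breach 5.2.1 from day 1.* Section 4.2 attaches the 10 mg limit to the same notion of chronic use, and reading 5.2.1 in line with it removes the breach. What remains is that 5.2.1 does not repeat the limit.
- *Men given prohibited agents leave the per-protocol population.* Section 8.4 defines that population by receiving the prescribed dose and not dropping out early; it does not mention prohibited medication.
- *Treatment of immune events will be delayed.* Nothing shows this, and Appendix 3 leaves steroid use for colitis to the investigator's judgment.

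The unseen algorithm figures may also contain a retreatment rule. Surviving text in Appendix 5 refers back to the protocol's own retreatment criteria, which makes the wording of those criteria matter more.

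**Conclusion.** The point holds in limited form, and the wording should be corrected. The restart rule in 5.1.3 and the steroid note in 5.1.5.2 can give opposite dosing decisions for a man whose held event has settled while he is still on systemic steroids, provided the event is one that 5.1.5.1 does not end. How many men this concerns cannot be stated from the documents. Separately, the unqualified bar on immunosuppressants in 5.2.1 does not fit algorithms that name infliximab and mycophenolate mofetil, and the steroid limit is worded differently across 4.1, 4.2 and 5.2.1.

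This rests on the text as read; the algorithm figures could narrow the gap but could not be examined. The primary endpoint, sample size and error rates do not depend on it.

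**What to change.** Reconcile the sections.

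1. In 5.1.3, state whether the steroid condition in the 5.1.5.2 note applies to restart after every event or only after endocrinopathies, and cross-refer the two sections.
2. Reconcile the 5.2.1 list with the IRAE treatments named in the appendices, so that a site can tell whether an agent used under an algorithm is permitted.
3. Use one steroid limit, worded the same way, in 4.1, 4.2 and 5.2.1, and define what counts as chronic use.

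Which restart condition and which limits are right is for the sponsor and its medical reviewers. The cost is a wording amendment with the usual approvals; no visit, sample or analysis changes.
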